## Summary of the Proposal

Research Topic:	A Multi-center, Retrospective Registry Study on the Safety of Hakim Programmable Shunt System
Research Purpose:	This study aimed to collect safety information from subjects implanted with a shunt system (trade name: Hakim Shunt Programmable System) produced by Codman & Shurtleff, Inc. of the United States. Device safety would be assessed based on all the adverse events that occurred within one year after the subjects implanted the catheter.
No. of Subjects:	130
No. of Research Centers:	About six research centers
Research Design:	
This study was designed to be single arm, multi-center, observational and retrospective trial. It is designed to gather information from actual clinical practice from the clinical records of patients in relation to the one-year clinical safety to the use of implant of Hakim programmable shunt system.
 
A total of 130 patients would be retrospectively enrolled. Information would be collected on adverse events of subjects enrolled within one year after the implantation of the Hakim Shunt Programmable System from April 01, 2017 to August 31, 2019.
 
The following information would be collected from subjects' medical records or hospitals' databases (if any):
 

1. General condition of the subjects

2. Intraoperative condition and shunt system implantation

3. Information on the shunt system product

4. Adverse events of subjects within one year after the operation and classification of the adverse events

5. Relevant examinations in case of postoperative infection

6. Other adverse event-related information (except anticipated adverse events)

Research Duration:	2019-2020
Inclusion Criteria:	
Subjects who met all of the following inclusion criteria would be enrolled:
 

1. The informed consent was exempted by the Ethics Committee of a research center. Either a subject or his/her legal representative signed the informed consent form (ICF) prior to enrollment.

2. A subject had an indication suitable to use Hakim Shunt Programmable

	
System.
 
3. A subject received a Hakim Shunt Programmable System at least one year ago.

Exclusion Criteria:	
Subjects who met any of the following exclusion criterion were excluded:
 
 
1. A subject didn't have an indication suitable to use the product.
 
2. A subject was known to be allergic to a component or ingredient of the product to be implanted, including silicone tubing and other components.
 
3. According to the comprehensive judgment of an investigator, a subject had an infection of the implant site when the shunt system was implanted, such as ventriculitis, meningitis, peritonitis, and local implant skin infection.
 
4. A subject was simultaneously implanted with another shunt system different from Hakim Shunt Programmable System.
 
5. A subject had a contraindication of the shunt operation.
 
6. A subject had uncorrected coagulopathy or any bleeding disorder.
 

Endpoint	
 
1. Non-infection rate of a subject within one year
 
2. Type and incidence of adverse events of a subject within one year
 

### Schedule of Data Collection Form

	Screening	Preoperative	Operation	Postoperative follow-up
Time of data collection	NA	-30 to -1 days	0	Days 1-365
Signed the ICF (if applicable) 	X			
Review of inclusion and exclusion criteria	X			
Medical History		X		
Laboratory examination		X		X+
Operative process			X	
Device application record			X	
Adverse events 			X*	X*
Serious Adverse Events			X*	X*
End of study/exit			X	X
Record of concomitant medication 		X*	X*	X*
Record of concomitant treatment 			X*	X*

+	Suspicious or proven infection
*	If any

Notes: 1. The ICF (if applicable) needed to be completed before screening.

2. A postoperative anticipated adverse event was not counted as an adverse event.

3. Only antibiotics and medications related to postoperative adverse events were recorded. Only the administration of antibiotics within seven days prior to the operation was recorded.

4. Only the treatment and operation associated with postoperative adverse events were recorded.

## Abbreviations:

AE	Adverse events
CRF	Case Record Form
CV	Curriculum Vitae
EC	Ethics Committee
ICF	Informed Consent Form
IFU	Instructions for Use
GCP	Good Clinical Practice
NMPA	National Medical Products Administration
SAE	Serious adverse event
SDV	Source data verification
UADE	Unanticipated adverse device effect

## 1 Introduction

### 1.1 Background and principle

Abnormal enlargement of part or all of subarachnoid space or ventricles, the abnormal accumulation of cerebrospinal fluid (CSF) in subarachnoid space or ventricles is called hydrocephalus. It is a circulation disorder of CSF caused by many pathological reasons. A shunt system mainly drains CSF from the accumulation site to the abdominal cavity, the lumbar cistern, and the atria through a catheter so as to address dilated ventricles and alleviate the pressure on the brain.

The earliest permanent CSF shunt operation occurred in 1893. A glass catheter was placed in a lateral ventricle of a patient with hydrocephalus, the end of which was placed under the skin. The head circumference of the patient was significantly reduced after the operation. The principle of modern shunt operation can be dated back to the 1870s. Ventriculo-peritoneal shunt operation had become a common treatment for hydrocephalus. China released *Specialist Consensus on the Standardized Treatment of Hydrocephalus in China* in 2013, which regarded CSF shunt as an important operation for hydrocephalus and proposed suggestions on technical key points.

However, in terms of the treatment of neurosurgical diseases, the incidence of complications of shunt operations is the highest, mainly including shunt infection, obstruction or rupture of a shunt catheter, displacement of an intracranial or abdominal shunt catheter, excessive or insufficient drainage of CSF, intracranial hemorrhage, and epilepsy. Infection is a common complication and important cause of revision. Its incidence rate is 3-29%. Approximately 90% of the cases occur within one year after the operation. If it is combined with ventriculitis, the mortality rate can be as high as 30-40%. For children, even if the infection can be controlled, long-term complications, such as epilepsy, cognitive impairment, and physical and delayed psychological development, may occur.

According to the analysis of recent literature, among a total of 8,588 shunt operations (3,291 cases with an antibiotic-impregnated catheter, 5,297 cases with a non-antibiotic-impregnated catheter), the postoperative infection of normal shunt system was 7.2%.

In addition to infection, complications of CSF shunt operations include excessive and insufficient drainage of CSF associated with pressure regulation; obstruction of the shunt catheter, usually due to a poor position of an intracranial shunt catheter, the accumulation of red blood cells or brain tissues in the shunt pump, or wrapping of a shunt catheter by abdominal omentum majus; rupture of shunt catheter, mostly occurring at the junction of the catheter and the pump and a subcutaneous area; and rare complications, such as displacement of a shunt catheter, wound, intracranial hemorrhage, and symptoms of Parkinson's Disease.

Hakim Programmable Shunt System manufactured by Codman & Shurtleff, Inc. in the United States constitute of a systemic silicon catheters and programmable valves. Hakim Programmable Shunt System has been safely used around the world for more than a decade. However, there is a lack of data on the safety of the product in long-term follow-up and clinical application in the Chinese population.

### 1.2 Research-related devices

Devices verified in this study were programmable shunt system catheters (trade name: Hakim programmable shunt system) manufactured by Codman & Shurtleff, Inc., U.S.A. Its registration number is G.S.Y.J.X. (J) 2017 3661104. Please refer to the Appendix 1 for the product specifications and models in this study.

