## **5. Objectives and Endpoint**

### **5.1. Objectives**

The objective of this study is to assess the safety of the Hakim programmable shunt system.

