### 6.2 Inclusion criteria

Subjects who met all of the following inclusion criteria would be enrolled:

1. The informed consent was exempted by the Ethics Committee of a research center. Or a subject or his/her legal representative signed the informed consent form (ICF) prior to the enrollment;
2. A subject had an indication suitable to use Hakim programmable shunt system;
3. A subject received a Hakim Shunt Programmable System at least one year ago.

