### 6.3 Exclusion criteria

Subjects who met any of the following exclusion criterion were excluded:

1. A subject didn't have an indication suitable to use the product;
2. A subject was known to be allergic to a component or ingredient of the product to be implanted, including silicone tubing and other components;
3. According to the comprehensive judgment of an investigator, a subject had an infection of the implant site, when the shunt was implanted, such as ventriculitis, meningitis, peritonitis, and local implant skin infection;
4. A subject was simultaneously implanted another shunt system different from Hakim programmable shunt system;
5. A subject had a contraindication of the shunt operation;
6. A subject had uncorrected coagulopathy or any bleeding disorder.

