### **7.3 Operation period (Day 0, the day of operation):**

The following information needed to be collected and recorded:

1. Operation: date of surgery, surgeon, surgical procedure, start and stop time of the operation, blood loss during the operation, medications, intraoperative complications, intraoperative shunt, and combined treatment;
2. Record of devices used during the operation: type, No. and batch No. of the cerebral ventricular shunt catheter; type, No. and batch No. of the pressure regulating valve; and type, No. and batch No. of shunt catheters at the abdominal cavity/the lumbar cistern/ the atria.

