#### **Analysis population**

The primary analysis population for this study is the Per Protocol (PP) populations. The PP population will include all subjects who meet the inclusion/exclusion criteria

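### Does the wide model list in Appendix 1 leave it unclear which implants qualify a subject?

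*Combined protocol and SAP*

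**What the plan says.** Section 1.1 says the Hakim programmable system is made up as follows: "constitute of a systemic silicon catheters and programmable valves". Section 1.2 identifies the device in these words: "Devices verified in this study were programmable shunt system catheters (trade name: Hakim programmable shunt system" (the bracket then closes and the manufacturer is named). It gives a single registration number and then the cross-reference: "Please refer to the Appendix 1 for the product specifications and models in this study".

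The text that decides who is studied uses the trade name alone:

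- Objective (5.1): "The objective of this study is to assess the safety of the Hakim programmable shunt system".
- Inclusion criterion 3 (6.2): "A subject received a Hakim Shunt Programmable System at least one year ago".
- Exclusion criterion 4 (6.3): "A subject was simultaneously implanted another shunt system different from Hakim programmable shunt system".
- Data extraction (11.4): investigators are asked to abstract the records of every patient at their centre who had the Hakim programmable system implanted.

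On data and analysis, section 7.3 records, among other items, "type, No. and batch No. of the pressure regulating valve". The analysis population paragraph in 10.6 reads: "The PP population will include all subjects who meet the inclusion/exclusion criteria". Section 11.3.2 requires the monitor to check all eligibility criteria and the use of devices for 100% of subjects. Section 12.5 makes any breach of eligibility a primary violation, confirmed jointly by an investigator, a data analyst and the sponsor.

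**The concern.** Section 1.2 is where a reader looks to learn what the study device is, and it sends that reader to a list much wider than a programmable shunt. Appendix 1 sets Precision valves beside programmable ones as separately named products. It also includes Uni-Shunt and James L-P shunts, catheters, connectors and surgical tools. Nothing says that the list is wider than the study device or which codes qualify.

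If a centre took the appendix as the definition, a Precision-valve recipient would be in. Under the description in 1.1, the same patient would be out. Exclusion criterion 4 raises the same question, because it turns on whether a second shunt differs from the study system.

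The analysis population follows from the criteria, so the denominator of both primary endpoints would depend on the reading. Valve type also bears on the adverse-event endpoint. Section 1.1 links over- and under-drainage to pressure regulation, and section 10.1 lists excessive drainage and failure of the programmable system among the events counted.

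**Working it through.** **1. What Appendix 1 contains, by row label**

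| Label | Rows |
|---|---|
| PROG or PROGRAMMABLE | 15 |
| CHPV | 6 |
| PREC or PRECISION | 60 |
| PV | 30 |
| NP | 15 |
| Uni-Shunt | 13 |
| James L-P | 3 |
| Surgical tools | 14 |
| #N/A | 3 |
| Other components | 64 |
| **Total** | **223** |

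One row, a Hakim valve introducer entry, could be counted as a tool or as a component. Nothing turns on it.

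**2. How many codes are programmable**

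The documents do not define CHPV, PV or NP. Only the 15 PROG rows are settled by their label.

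- Adding CHPV gives 15 + 6 = 21.
- Treating PV as equally unresolved gives 21 + 30 = 51.
- Treating NP the same way gives 51 + 15 = 66.

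The pressure grades help. A grade appears on all 30 PV rows, all 15 NP rows and 45 of the 60 Precision rows, and on none of the 21 PROG or CHPV rows. That pattern makes it likely that PV and NP belong with Precision, but this is inference. The mismatch does not depend on it, because the Precision, Uni-Shunt and James L-P rows carry other product names outright.

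**3. Which rows could change who is enrolled**

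The tools cannot: nobody receives a shunt system by being operated on with a passer or a needle. The catheters, reservoirs and connectors can be parts of a programmable system as 1.1 describes it. That leaves the valves under other names (60 + 30 + 15 = 105 rows, on the likely reading of PV and NP) and the 16 separately named shunts.

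**4. Whether the operative text admits those products**

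Inclusion criterion 3 requires receipt of the programmable system. A Precision valve, Uni-Shunt or James L-P shunt does not meet those words. Exclusion criterion 4 compares a second shunt with the programmable system, so a separately named shunt system is different on its face. Neither criterion mentions Appendix 1. Section 7.1.3 counts a subject as enrolled only when every inclusion criterion is met. The purpose (3.2), the objective (5.1) and the extraction instruction (11.4) agree.

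**5. Whether an error could be found**

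Yes. The valve's type and number are recorded (7.3), device use and eligibility are checked for all subjects (11.3.2), breaches are classed as primary violations (12.5), and the analysis population requires the criteria to be met (10.6).

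**6. Precision, as illustration only**

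The plan's figure in 10.3 reproduces: N(1) = 130 × exp(−(0.072 + 0.10)) = 109.5 (stated as 109), and the half-width is 1.96 × √(0.928² × 0.072 / 109) = 4.7%. The same formula stays below 5% down to 114 enrolled: N(1) = 114 × exp(−0.172) = 96.0, half-width 4.98%. So if some of the 130 proved ineligible on valve type and were removed, up to 130 − 114 = 16 could go before the precision target was missed. The documents give no reason to expect any particular number.

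**The case for a change.** The strongest case for acting is that 1.2 is the section meant to identify the device, and it attaches the trade name to the wider list. Verification and violation review test compliance with a definition. They cannot say which of two definitions applies, and different centres could each apply a different one consistently. The report goes to the regulator in support of a registration extension for a named product (10.7), and one clarifying sentence would cost almost nothing.

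Part of this stands. The list is wider than the study device, the plan does not say why, and no passage marks the qualifying codes. A registered-range list is a natural explanation, given the registration number in 1.2 and the purpose of the report, but the documents do not confirm it.

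The step from there to an ambiguous cohort does not stand. It needs a catalogue that no criterion cites to override the plain words of the criteria that govern enrolment. The reference to catheters in 1.2 is not a rival definition either. Section 3.2 likewise speaks of subjects being implanted with the catheter while naming the whole system, and the document reads as a translation. The two possible remedies also point in opposite directions: narrow the list to programmable codes, or widen the title and objective to the full range. The criteria already adopt the first.

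**Conclusion.** This is a gap in detail that sites and analysts can fill sensibly, and no change to the plan is needed. Following the criteria as written gives a cohort of programmable-system recipients, and the data already collected allow each subject's valve to be checked. The mismatch lies in the catalogue: 15 rows are certainly programmable by label, 60 Precision rows and 16 other shunt rows are certainly named as something else, and 51 rows (6 CHPV, 30 PV, 15 NP) carry undefined labels. None of these counts is a number of patients. The device mix is not given, so no effect on the infection-free rate or the adverse-event incidence can be calculated, and none is shown.

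The conclusion assumes that centres read criterion 3 in its ordinary sense, that the valve type and number in 7.3 are recorded completely enough to identify the product, and that someone who knows the product line can tell a programmable code from the others. A note that the appendix is the registered range, if that is so, would tidy the document without altering the design or the analysis.

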## **2. Benefits/Risks**

### **2.1 Benefits**

Hakim programmable shunt system serves as the shunt system of hydrocephalus treatment. Hydrocephalus shunt operations can alleviate or eliminate hydrocephalus and improve clinical symptoms and signs. Meanwhile, retrospective collection of data and experience of clinical safety can be used as a reference for investigators and enterprises and conducive to the diagnosis and treatment of future subjects. However, such data and experience had no extra benefits for the participants in this study.

### **2.2 Risks**

This is a retrospective study. It did not intervene in subjects' normal treatment. It objectively collected patients' clinical data. Hence, there were no additional risks associated with participating in this study.

## **3 Research purpose**

### **3.1 Indications**

Hakim programmable shunt system: Hakim programmable shunt system serves as the shunt system of hydrocephalus treatment.

### **3.2 Purpose**

This study aimed to collect safety information from subjects implanted with a programmable shunt system (trade name: Hakim programmable shunt system) produced by Codman & Shurtleff, Inc. of the United States. Device safety would be assessed based on all the adverse events that occurred within one year after the subjects were implanted with the catheter.

## **4. Research Design**

### **4.1 Basic design**

This study was designed to be single arm, multi-center, observational and retrospective. It is designed to gather information from actual clinical practice from the clinical records of patients in relation to the one-year clinical safety to the use of operation of Hakim programmable shunt system. The treatment date would be defined as the implant date of the Hakim programmable shunt system. The study period includes a general history period that includes up to 30 days prior to the treatment date and a follow-up period of up to 365 days post implant operation. A total of 130 patients would be enrolled and adverse events would be collected for subjects enrolled within one year after the implantation of Hakim programmable shunt system from April 01, 2017 to August 31, 2019, through case review or hospital database (if any).

### **4.2 Data collection**

The following information would be collected from subjects' medical records:

1. General condition and medical history of the subjects

**2. Intraoperative condition and shunt system implantation**

**3. Information on the shunt system product**

**4. Adverse events of subjects within one year after the operation and classification of the adverse events**

**5. Relevant examinations in case of postoperative infection**

**6. Other adverse event-related information (except anticipated adverse events)**

Information on adverse events would be collected. And the safety of clinical application of the product would be assessed.

## **5. Objectives and Endpoint**

### **5.1. Objectives**

The objective of this study is to assess the safety of the Hakim programmable shunt system.

### **5.2 Primary Endpoint**

1. Non-infection rate of a subject within one year post implant

2. Incidence of adverse events within one year post implant

### **5.2 Safety indicators**

The incidence of adverse events was observed in line with the IFU. Key attention should be paid to:

- Obstruction of a cerebral ventricular catheter
- Falling out of a programmable shunt system
- Poor position of a catheter
- Intestinal perforation, abdominal and pseudocysts, umbilical fistula, pseudo-acute appendicitis, infection, and ascites
- Subcutaneous twist, rupture, distal obstruction, and distal retraction from the abdominal cavity
- Failure of a programmable shunt system
- Mechanical failure
- Obstruction or infection of the shunt path
- Leakage of CSF in an implanted programmable shunt system
- Excessive drainage
- Damage of intracranial or abdominal tissue
- Fibrous adhesion

## 6 Study Population

### 6.1 Selection of subjects

Subjects who received a hydrocephalus shunting operation between April 01, 2017 and August 31, 2019 and met the inclusion criteria were enrolled. As this was a retrospective study, it would apply for the exemption of informed consent from the Ethics Committee of a center. For the centers which did not exempt informed consent, the informed consent process would be completed prior to the start of data collection, either by telephone or by anyway approved by the Ethics Committee.

### 6.2 Inclusion criteria

Subjects who met all of the following inclusion criteria would be enrolled:

1. The informed consent was exempted by the Ethics Committee of a research center. Or a subject or his/her legal representative signed the informed consent form (ICF) prior to the enrollment;
2. A subject had an indication suitable to use Hakim programmable shunt system;
3. A subject received a Hakim Shunt Programmable System at least one year ago.

### 6.3 Exclusion criteria

Subjects who met any of the following exclusion criterion were excluded:

1. A subject didn't have an indication suitable to use the product;
2. A subject was known to be allergic to a component or ingredient of the product to be implanted, including silicone tubing and other components;
3. According to the comprehensive judgment of an investigator, a subject had an infection of the implant site, when the shunt was implanted, such as ventriculitis, meningitis, peritonitis, and local implant skin infection;
4. A subject was simultaneously implanted another shunt system different from Hakim programmable shunt system;
5. A subject had a contraindication of the shunt operation;
6. A subject had uncorrected coagulopathy or any bleeding disorder.

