### 7.1 Screening and enrollment

#### 7.1.1 Screening of subjects

Qualified and authorized investigators or clinical study coordinators reviewed the medical records of subjects to screen subjects eligible for this study.

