### **7.1.3 Enrollment of subjects**

If a subject met all the inclusion criteria and did not meet any exclusion criterion, he/she could be included in the retrospective analysis cohort. Subjects could be considered as enrolled in this study only if they met the following requirements:

- 1) A subject met all the inclusion criteria and did not meet any exclusion criterion; and
- 2) The ICF was signed (in terms of a research center that did not waive informed consent).

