### **7.4 Postoperative follow-up period: Days 1-365**

An adverse event (except an anticipated adverse event) discovered during the review of postoperative history or hospital database (if any) should be recorded:

The date, description, concomitant therapy, and outcome of an adverse event, information related to the operation and the product, not matter the implanted part was taken out due to an adverse event, and concomitant medication and treatment should be recorded.

Additional records were required for the following special adverse events:

1. Infection: Infection site which is usually classified into intracranial, skin, and abdominal infections. For intracranial infection, date of infection, white blood cell count, red blood cell count, neutrophilic granulocyte count, hemoglobin content, alanine aminotransferase (ALT), aspartate aminotransferase (AST), C-reactive protein, blood glucose, traits and color of CSF, cell count, Pan's test results, contents of protein, sugar, and chloride in CSF, bacterial culture type, and bacterial susceptibility to rifampicin and clindamycin should be recorded. For skin infection and abdominal infection: white blood cell

count, red blood cell count, neutrophilic granulocyte count, bacterial culture type, and bacterial susceptibility to rifampicin and clindamycin should be recorded.

2. Obstruction of catheter: site, reason (judged by an investigator), and nature of obstruction should be recorded.

3. Leakage of CSF: date and position of leakage should be recorded.

4. Mechanical failure: type of mechanical failure should be recorded, including falling out, displacement, twisting, and rupture.

A patient who died within one year was still considered as a complete case. The form of SAE should be completed. And the death should be specified in this study endpoint table.

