# **10 Statistical Methods**

## **10.1 Primary endpoint**

The primary endpoint of the study is:

Non-CSF infection within one year post implant.

Incidence of adverse events within one year post implant, which includes:

- Obstruction of a cerebral ventricular catheter
- programmable shunt system slipping
- Poor position of a catheter
- Intestinal perforation, abdominal and pseudocysts, umbilical fistula, pseudo-acute appendicitis, infection, and ascites caused by catheter
- Subcutaneous twist, rupture, distal obstruction, and distal retraction from the abdominal cavity
- Failure of a programmable shunt system

- Mechanical failure
- Obstruction or infection of the shunt path
- Leakage of CSF in an implanted programmable shunt system
- Excessive drainage
- Damage of intracranial or abdominal tissue
- Fibrous adhesion related to distal catheter

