## 10.2 General considerations

The primary analysis will be descriptive in nature and will be based on information in the data collection form.

The extraction of the data from the medical records will be done by the investigators who care for the patients; in this way, the possible limitation of the study that is normally observed in other studies of review of clinical histories in which the information can be interpreted incorrectly is minimized.

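### Exclusion 3 (infection at implantation) is judged from charts that already hold the one-year outcome, with no limit to baseline evidence and no required count of patients screened out

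*Combined protocol and SAP*

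**What the plan says.** All references are to the combined protocol and SAP.

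- **Criterion.** Section 6.3, item 3, applies when "According to the comprehensive judgment of an investigator, a subject had an infection of the implant site, when the shunt was implanted". Its examples are ventriculitis, meningitis, peritonitis and local skin infection at the implant. The summary of the proposal repeats the criterion.
- **Timing.** Section 6.2 requires that "A subject received a Hakim Shunt Programmable System at least one year ago".
- **Screening.** Under section 7.1.1, investigators or study coordinators "reviewed the medical records of subjects to screen subjects eligible for this study". Under section 7.1.3, a patient who passes all criteria is one of whom it is said that "he/she could be included in the retrospective analysis cohort".
- **Extraction.** Section 10.2 states: "The extraction of the data from the medical records will be done by the investigators who care for the patients". The reason given is to reduce misreading of the records.
- **Endpoint.** Section 5.2 (Primary Endpoint) has "Non-infection rate of a subject within one year post implant"; section 10.1 has "Non-CSF infection within one year post implant". Section 7.4 asks for the site of each postoperative infection: "Infection site which is usually classified into intracranial, skin, and abdominal infections".
- **Analysis set.** Section 10.6 names one population, per protocol, made up of subjects who satisfy the eligibility criteria. The one-year infection-free rate is estimated by Kaplan-Meier.

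**The concern.** In a prospective study, eligibility is settled before the outcome exists. Here the person applying exclusion 3 has a chart that runs through the following year. An infection first noted a few days or weeks after surgery raises a real question: was it already there at implantation? The plan leaves the answer to overall judgment and does not say that only baseline findings may be used. If the answer is yes, an event disappears from a primary endpoint and the patient disappears from the denominator.

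The conditions named in exclusion 3 are largely the same as those counted afterwards. Ventriculitis and meningitis overlap with the endpoint even if it means CSF infection only. Peritonitis and skin infection overlap too if it means any infection.

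The report is to support extension of the product's registration (section 10.7). Without counts of exclusions by criterion, its reader could not tell whether exclusion 3 moved the rate.

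**Working it through.** **1. Does any provision limit the evidence or make the exclusions visible?**

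| Section | What it provides | What it leaves open |
|---|---|---|
| 6.1 | Patients operated on in the window who met the inclusion criteria were enrolled | No tally of those not enrolled |
| 7.2 | Preoperative blood tests, including white cells and C-reactive protein, and antibiotics in the prior seven days | Helps find infected patients wrongly kept; lists no preoperative CSF test or culture, and is not made the basis for exclusion 3 |
| 11.3.2 | All criteria verified for 100% of subjects | Works from subjects' CRF entries; does not state that it reaches patients screened out |
| 11.3.3 | CRF completed soon after screening | Requires no form or reason for a patient screened out |
| 11.4 | Extraction asked for all patients implanted for the study | Requires no log or count of exclusions |
| 12.5 | Eligibility violations are primary violations | An unrecorded exclusion leaves nothing to detect |

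Together these reduce the risk of selective inclusion. None restricts the evidence for exclusion 3, and none requires exclusions to be counted or explained.

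**2. The plan's own precision figure (section 10.3).** Inputs: 130 enrolled, infection rate 7.2%, dropout 10%.

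- N(1) = 130 × e^−(0.072 + 0.1) = 109.5 (the plan states 109).
- Half-width = 1.96 × √(0.928² × 0.072 / 109) = 4.67 points (the plan states 4.7%).

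Both figures reproduce.

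**3. Effect of one reclassified infection.** The simple proportion is used here, ignoring censoring.

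- Expected infections: 130 × 0.072 = 9.36.
- Removing one infected patient from numerator and denominator lowers the rate by (1 − 0.072) / (130 − 1) = 0.72 points, and 0.72 / 4.67 = 15% of the half-width.

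**4. Illustration for k reclassified cases.** The values of k are assumptions; the documents give no basis for any of them.

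| k | Rate if not replaced, (9.36 − k)/(130 − k) | Shift (points) | Share of 4.67 | Rate if replaced to keep 130, (9.36 − k + 0.072k)/130 |
|---|---|---|---|---|
| 1 | 6.48% | 0.72 | 15% | 6.49% |
| 2 | 5.75% | 1.45 | 31% | 5.77% |
| 3 | 5.01% | 2.19 | 47% | 5.06% |

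The nominal interval narrows as events are removed. At k = 3, without replacement, the plan's formula gives about 4.0 points instead of 4.7, so the precision target would give no warning.

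**5. The opposite error.** If k infections truly present at implantation were counted as events, the rate would be (9.36 + k)/(130 + k): 7.91%, 8.61% and 9.29% for k = 1, 2 and 3, again about 0.7 points per case.

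**The case against.** The strongest reply is that the criterion already refers to infection present at implantation, so excluding a true postoperative infection would misapply it. Investigator judgment on eligibility is a legitimate choice, and section 10.2 gives a reason for using treating investigators to extract data. Sections 6.1 and 11.4 can be read as calling for all eligible patients, sections 11.3.2 and 12.5 police eligibility, and a screening log might sit in the monitoring plan that section 11.3.2 cites. The study is descriptive and has no pass/fail criterion (sections 10.2 and 10.4). Every shift shown above lies inside the half-width.

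Much of this stands. It limits the weight of the point and rules out any claim that the criterion is wrong in itself. It does not close the gap. When the onset of an infection is uncertain, an investigator can follow the criterion as written and still let the later course decide. The controls do not count or explain the patients removed. That a shift fits inside the half-width is no defence, because the interval describes sampling error and not selective removal of events.

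A reader might infer that investigators did remove early infections, or that the reported rate will be too low. The documents do not support either: they show that the route is open, not that it was used. Nor do they show that no screening log exists, only that these documents do not require one.

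**Conclusion.** The point holds as a gap in safeguards and transparency on a primary endpoint. Exclusion 3 permits outcome-aware judgment about infection at implantation, and the supplied documents neither confine the evidence to baseline nor require exclusions to be counted.

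The size is unknown. At the plan's assumed 7.2%, each reclassified infection would lower the rate by about 0.7 points, roughly 15% of the planned half-width. This rests on the 7.2% rate and on a simple proportion in place of the Kaplan-Meier estimate.

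No decision threshold depends on the rate, so the point does not undermine the study. It should be fixed because about 9 expected events leave little room for unseen losses and the remedy is cheap. Confidence is medium, chiefly because the monitoring plan was not available.

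**What to change.** 1. **Evidence rule.** Apply exclusion 3 only on findings or observations made, or specimens taken, on or before Day 0, whenever they were written up or reported. A later discharge summary describing an intraoperative finding would qualify. Count other infections in Days 1-365 that meet the endpoint definition as events.
2. **Accounting.** Report by centre the numbers implanted, screened and excluded under each criterion. For each exclusion under criterion 3, log the dated evidence, the date of any postoperative infection and the date of last follow-up.
3. **Sensitivity analysis.** Give a second Kaplan-Meier estimate that adds back patients excluded under criterion 3. Those with infection first documented in Days 1-365 count as events on that date; the others are censored at last follow-up. The two estimates together show how far exclusion 3 affects the result.

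**Cost.** Protocol wording, a log built from records the centres already review, and modest extra extraction for the patients excluded under criterion 3. The downside is that some infections truly present at implantation but without Day 0 evidence may be counted as events, raising the rate by about 0.7 points each.
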